Once diagnosed, in order to be treated, patients must see a physician and undergo the various tests and laboratory analyses mentioned above. The patient who engages in this process is considered to be "linked-to-care". However, many patients do not consult or quickly disengage from follow-up. A US study reported that 47% of patients who know their status do not link to the health care system.³ The often long delays between diagnosis and clinical management contribute to the current loss to follow-up. For example, one Canadian study reported delays of 66.3 months from initial diagnosis to referral to a specialty, an additional 1.5 months to seeing the specialist, and 6.8 months from initial visit to initiation of treatment.¹⁵ Another Canadian study reported loss-to-follow-up rates of 19% during evaluation, while a Scottish study noted that 16% of patients never made it to the first visit and 24% were lost after only one visit.^{16,17} It is therefore important to assess whether expediting management would allow more patients to initiate treatment by limiting disengagement from care.

The goal of the first project is to evaluate the feasibility of routine HIV and HCV screening using an opt-out approach in the CHUM emergency department and to determine the rate of new HIV and HCV diagnoses. A sub-analysis will focus more specifically on HCV in the Quebec equivalent of the baby boomers (1945-1975), since this is the group that was targeted in the United States.¹⁸ We also want to evaluate the effectiveness of linkage-to-care for people diagnosed with HIV or HCV and the speed with which these people are taken into care and put on treatment.

Hypothesis:

We believe that it is realistic to observe a proportion of new diagnoses greater than 1/1000 for HIV and 1/100 for HCV in the CHUM emergency department.

Objectives:

Primary objectives

1. To determine the prevalence of new HIV and HCV diagnoses among the patients visiting the CHUM emergency department
2. To determine the overall prevalence of HIV and HCV (new cases and known cases) among the patients visiting the CHUM emergency department

Secondary objectives

1. To determine the prevalence of new and known HCV cases among the "baby boomers" (41-73 years)
2. To determine the proportion of adherence of ED staff to the offer of HIV and HCV testing
3. To determine the proportion of patients "opting out" of routine HIV and HCV testing in the ED

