4. To determine the proportion of patients with a newly positive HIV or HCV test in the ED who attended a first appointment at 1 month
5. To determine the proportion who completed certain steps in the HIV and HCV care cascades at 1 or 3 months, namely confirmation of diagnosis (HIV and HCV: 1 month), liver fibrosis assessment (HCV: 3 months), and treatment initiation (HIV: 1 month and HCV: 3 months)
6. To define the organization of services needed to continue screening beyond the research project in terms of costs, nursing time, volume of tests and communication of results.

Design:

Cross-sectional study of ED patients with evaluation of the implementation of the screening program and prospective follow-up for 3 months of the positive cases.

Method:

Implementation: Preparatory meetings will be held with CHUM ED managers, medical leaders, and nurses to discuss issues associated with routine screening and to attempt to find solutions to anticipated barriers in advance. Following these discussions, ED triage staff, including day, evening and night staff, will be met for training on the importance of screening and the procedure that will be followed under this protocol.

Informational Tools:

Patient announcements

Information materials will be prepared to announce to CHUM ED patients that HIV and/or HCV testing will be performed. Posters will be put up in the ED and an information sheet will be given to patients at the time of registration.

Materials for Nurses:

The following items will be added to the triage form already in place in the ED: "Are you infected with HIV? Are you infected with HCV?", "Unless you decline, we will be performing a blood test for HIV (and/or) HCV today." These questions will simultaneously serve as a reminder for staff to offer the test and as a data collection form for investigators.

Pre-printed orders for HIV and HCV testing will also be created with the name and license number of one of the investigators.

Laboratory Tests:

The tests used will be the routine CHUM tests (ARCHITECT HIV Ag/Ab combo and ARCHITECT anti-HCV assay). These were chosen over rapid tests because

they are less expensive and more sensitive, they are more representative of what might be widely available in the event of a provincial rollout of ED screening, and there are no licensed rapid tests for HCV in Canada.

Screening:

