At triage, patients will be advised that they will be tested for HIV and/or HCV unless they refuse to be tested or are already known to be infected with HIV and/or HCV. If a patient is known to be infected with HIV or HCV, they may be tested for the virus whose status is unknown. The time required to educate the patient and obtain answers to questions will be measured for a sample of patients after an initial period of staff adjustment. The nurse performing the collection will be the same nurse who performs the patient's regular blood work. She will use the pre-printed orders for this purpose. The physician in charge of receiving the results will be one of the study investigators. Patients who do not have to have their blood drawn for their health problem will still be offered the test.

Results management:

Patients will be notified that they will receive their test results without specifying how. As opposed to having all patients travel or announcing all results over the phone, this strategy is intended to ensure that patients called back for an appointment do not spontaneously understand that they are infected with HIV or hepatitis C when they are home alone, while limiting the number of patients who will have to travel since the vast majority of tests will be negative.

The research nurse will have access to the results of all tests performed via the CHUM computer system. In the event of a positive result (confirmed by the Laboratoire de santé publique du Québec (LSPQ) for HIV and by the CHUM laboratory +/- the LSPQ as needed for HCV), she will notify one of the investigators who will contact the patient in person, if he or she is still present at the hospital, or by giving him or her an appointment, if he or she has left. The research nurse will organize a follow-up with one of the CHUM's specialized clinic coordinators, taking into account the diagnosis, the type of clientele and the person's choice. The time required to reach the patient and plan the liaison with the care team as well as the mode of communication used will be noted. If the result is negative, the physician will delegate the research nurse to contact the patient to give him or her the result, either by telephone or by mail, depending on the method of communication available in the hospital file.

Health system linkage:

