The research nurse will check the hospital's computer system to see if the patient has been seen in a specialty clinic within one month of the positive test announcement. If not, the research nurse will follow up with the patient by phone to see if they have been seen outside the hospital for this new diagnosis. If after three attempts to call, the patient is not reached, they will be considered not linked to the health care system. For HIV patients, she will check for confirmatory

serology, viral load, and CD4 count and whether treatment has been initiated. For HCV, she will verify that RNA testing and, if applicable, genotyping have been performed. For chronic HCV patients, she will assess at 3 months whether liver fibrosis has been assessed and whether treatment has been prescribed.

Eligibility criteria for the cross-sectional HIV/HCV screening component of the study:

Inclusion criteria :

Individuals between the ages of 18 and 73 years consulting the CHUM emergency department regardless of the time of consultation.

Exclusion criteria :

Persons unable to refuse the test, notably because of their medical condition leading them to consult the emergency room.

If the person's condition improves during the emergency room visit, they may be offered screening at that time.

Eligibility criteria for the linkage-to-care of HIV/HCV-infected patients component of the study:

Inclusion criteria:

- Patient who has agreed to HIV or HCV test(s) in the UHC emergency department.
- Aged 18 years to 73 years
- Tested positive for HIV and/or HCV
- Able to consent and sign the information and consent form

Outcomes:

Primary outcomes

1. Prevalence of unknown HIV or HCV infections in the CHUM emergency department during the study period: positive tests / tests performed in unknown patients with HIV or HCV
2. Overall prevalence of HCV and HIV during the study period: (positive tests + known positive cases) / (tests performed + known positive cases)

Secondary outcomes

1. For HCV, among baby boomers (1945-1975 or 43-73 years)
 - a. Prevalence of new cases (positive tests/tests performed)
 - b. Overall prevalence (positive tests + known positive cases) / (tests performed + known positive cases)
2. Staff adherence: (tests performed, refused or known positive) / (eligible patients)
3. Proportion of patient opt-outs: tests refused / (tests performed + tests refused)

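### Primary outcome 1 and secondary outcome 1a: with no check for earlier diagnosis after triage and no stated HCV confirmation method, the HCV new-case count can include earlier-diagnosed, treated or non-current HCV

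*Combined protocol and SAP*

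**What the plan says.** - **Outcome.** Outcomes, primary item 1, is headed as the prevalence of unknown infections and computed as "positive tests / tests performed in unknown patients with HIV or HCV". Secondary item 1a applies the same ratio to HCV in baby boomers and calls the result new cases. Primary item 2 and secondary item 1b add known cases to numerator and denominator.
- **Target.** The Hypothesis section expects new diagnoses "greater than 1/1000 for HIV and 1/100 for HCV".
- **Assays.** Laboratory Tests names the "ARCHITECT HIV Ag/Ab combo and ARCHITECT anti-HCV assay".
- **Prior status.** The triage form asks "Are you infected with HIV? Are you infected with HCV" (Materials for Nurses). Patients are tested unless they refuse "or are already known to be infected with HIV and/or HCV" (Screening). Data collection takes the number of known patients from the triage sheets.
- **Confirmation.** Results management has HIV positives confirmed at the LSPQ, and HCV positives confirmed "by the CHUM laboratory +/- the LSPQ as needed for HCV". It gives no HCV method.
- **RNA.** Health system linkage states: "For HCV, she will verify that RNA testing and, if applicable, genotyping have been performed". Secondary outcome 5a lists qualitative RNA as a one-month cascade step. Data collection places RNA with the management results of the infected-patient cohort, apart from the screening and confirmatory results taken for everyone screened. Entry to that cohort requires signed consent.

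**The concern.** The label and the rule do not describe the same quantity, for two separate reasons.

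**History.** Someone whose HCV was treated in the past can truthfully answer no to a question about being infected now. Someone who does not disclose a diagnosis gives the same answer. Both are then tested and, if positive, enter the numerator as new. The plan describes no later look-up of earlier results or treatment.

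**Infection.** If confirmation before the result is announced does not include RNA, the numerator counts antibody positivity, whether or not infection is current. This part also reaches primary outcome 2 and secondary outcome 1b, which use the same positive-test term.

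At stake are the reading of the HCV result against 1/100, the baby-boomer sub-analysis and the cost per new diagnosis (Analyses). The limitations section makes a second, multicentre project depend on meeting the initial targets, so the reading has a consequence although the analyses are descriptive. That section discusses refusal, shift differences, the window period and generalisability, but not earlier or treated HCV.

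**Working it through.** **1. The plan's own figure.** Sample size assumes 1/100 undiagnosed HCV and 4,000 subjects, so 40 positives. Wald interval: 0.01 ± 1.96 × √(0.01 × 0.99 / 4000) = 0.01 ± 0.0031, or 0.69% to 1.31%. This matches the stated 0.7% to 1.3%, so the arithmetic is not at fault. The exact (Clopper-Pearson) interval for 40/4,000 is 0.72% to 1.36%.

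**2. Which mechanism reaches which outcome.** Let K be the known cases and h the positives found to have an earlier diagnosis.
- Outcomes 1 and 1a: both mechanisms apply.
- Outcomes 2 and 1b, history: moving h positives to previously diagnosed gives ((40 − h) + (K + h)) / ((4000 − h) + (K + h)) = (40 + K)/(4000 + K). Nothing changes.
- Outcomes 2 and 1b, infection: r RNA-negative positives lower the estimate by r/(4000 + K).

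**3. Illustration for outcome 1.** The fraction f of the 40 positives that are not new active infections is assumed; the documents give none. Prevalence is 40(1 − f)/4000. The cost multiplier is 40/(40 − x) if cost is reported for HCV alone and 44/(44 − x) if pooled with 4 expected HIV cases, where x = 40f.

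| f | x | Cases | Prevalence (exact 95% CI) | Cost, HCV alone | Cost, pooled |
|---|---|---|---|---|---|
| 0 | 0 | 40 | 1.00% (0.72–1.36) | 1.00 | 1.00 |
| 15% | 6 | 34 | 0.85% (0.59–1.19) | 1.18 | 1.16 |
| 25% | 10 | 30 | 0.75% (0.51–1.07) | 1.33 | 1.29 |
| 40% | 16 | 24 | 0.60% (0.38–0.89) | 1.67 | 1.57 |

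Taking reclassified cases out of the denominator as well hardly matters: 34/3994 = 0.851% and 24/3984 = 0.602%. Against the planned half-width of 0.3 points, the shift of 0.15 to 0.40 points is 0.5 to 1.3 half-widths.

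**4. Outcome 2.** With K = 80 (assumed), (40 + 80)/(4000 + 80) = 2.94%. With r = 6 it is 114/4080 = 2.79%; with r = 16 it is 104/4080 = 2.55%.

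**5. HIV.** About 4 positives are expected: 1.0 per 1000 (exact 0.3 to 2.6). One undisclosed earlier diagnosis gives 0.75 (0.2 to 2.2) and two give 0.50 (0.1 to 1.8). These shifts are small beside sampling error.

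**The case against.** - **The terms are not wholly undefined.** A reader might infer that the plan never says what unknown means. It does: the formula is explicit, patients known to be infected are not tested for that virus, and known status is recorded at triage. What is missing is any check beyond the patient's answer. This objection stands.
- **Confirmation might include RNA.** Secondary objective 5 has the cascade step "namely confirmation of diagnosis (HIV and HCV: 1 month", and outcome 5a lists qualitative RNA under that step. RNA at the earlier confirmation therefore cannot be excluded. The separate listing in Data collection points the other way, but only by inference. The infection part must stay conditional; the history part does not depend on it.
- **The three-month checks are for chronic HCV patients.** A reader might infer that the plan foresees positives without infection. The word may only separate chronic from acute infection. Genotyping only where applicable, after RNA, is better support, though not proof. That antibody positivity alone does not establish current infection is an assumption from general serology, not a statement in the documents.
- **The size is assumed.** The 15% to 40% range has no source in the plan, and one fraction merges two mechanisms. Even as counted, 40/4,000 does not show a prevalence above 1/100, and at 15% and 25% the exact interval still contains 1%. This stands: the range shows sensitivity and nothing more.
- **RNA data are already planned.** They are, for consenting patients. But outcome 5a as written tracks completion of the test, not its result, and nothing links the result to the primary outcome.

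**Conclusion.** The point holds for HCV. Followed as written, the rule can count undisclosed or previously treated HCV as new in outcomes 1 and 1a. If confirmation does not include RNA, it also counts positives without current infection in outcomes 1, 1a, 2 and 1b. Both mechanisms push new-case prevalence up and cost per new diagnosis down. If 1/100 means new antibody positivity, only the history part biases the comparison; if it means active infection, both can. The plan does not say which.

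A reader might infer that HCV prevalence will be overestimated overall. The documents do not support that: the limitations section notes that the window period lowers observed prevalence, and no net direction can be derived. Nor is a formal test affected, since the analyses are descriptive. Under the assumed 15% to 40%, the new-case estimate falls by 0.15 to 0.40 points, and only at the upper end does the exact interval lie wholly below 1/100. The cost multipliers depend on whether cost is reported per virus or pooled, which the plan does not state. For HIV the issue is limited to undisclosed earlier diagnoses and is small. This should be fixed; confidence is medium because the HCV confirmation method is unstated.

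**What to change.** 1. **History.** For outcomes 1 and 1a, count a confirmed positive as new only if no earlier diagnosis or treatment is found in OACIS or reported at the result appointment. Move the others to a previously diagnosed category, out of numerator and denominator. Report how many positives had their history checked.
2. **Infection.** State the HCV confirmation method. If it does not include RNA:
   - label outcomes 1 and 1a for HCV as new anti-HCV positivity, and report beside them the prevalence of new RNA-positive HCV among those tested, with best- and worst-case bounds for positives lacking RNA;
   - describe outcomes 2 and 1b as anti-HCV positive on screening or self-reported known HCV, and add a counterpart that replaces screen positives with RNA-positive screens, stating that known cases are as reported and untested.
3. **Target and cost.** State which measure is compared with 1/100, and give cost per new HCV case on both.

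**Cost.** The work is wording plus a record check on about 44 expected positives (40 HCV, 4 HIV) in a system the research nurse already uses. The consent exemption covers the screening tests, so history or RNA retrieval in positives who do not consent may need ethics-committee agreement. Diagnoses made elsewhere can still be missed. The RNA-based figure may be less favourable, and its bounds may be wide: each positive lacking RNA adds 1/4000 = 0.025 points, so 4, 8 or 12 of 40 (assumed) give widths of 0.10, 0.20 or 0.30 points. Antibody positivity should therefore remain as the complete-data measure.

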Universal HIV Screening and Targeted HCV Screening in Emergency Department

NCT03595527

The initial version of this protocol was approved in French by the Centre hospitalier de l'Université de Montréal institutional review board on March 6th, 2018. An investigator was added on June 20th, 2018. This is a translation of the latest version.

Dépistage universel du VIH et dépistage ciblé du VHC à l'urgence

Rational:

The cascade of care is a widely used concept in HIV. It is a way of representing a patient's progression from diagnosis to disease management. It is used to assess the quality of care provided, to identify barriers that limit patient progress, to focus research on these barriers, and to develop public health policies.^{1,2} The advent of effective treatments for HCV has made it possible to transpose the concept of the cascade to HCV, thus moving away from a research logic focused on optimizing the sustained virological response (SVR) of individuals to a logic of access to this virological response for all.¹ The two steps in the cascade that are most critical for the management of HCV in Quebec, as in other countries, are access to the screening test and linkage to the health care system. Problems with screening, linkage to the health care system and losses to follow-up throughout the cascade are estimated to reduce the effectiveness of treatment by up to 75%.³

HCV and HIV screening based on risk factors, according to Quebec and Canadian recommendations, does not allow for the identification of all cases. It is estimated that 44% of Canadians infected with HCV and 21% of Quebecers infected with HIV are unaware of their status.^{4,5} In addition, nearly 26% of HCV-positive patients do not obtain their test results and are therefore not managed (loss of follow-up between the test and the results).³ It is therefore important to evaluate new models of screening adapted to the Quebec healthcare system.

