4. Linkage of positive cases to a care team 1 month post-test (definition: attended at least one appointment).
5. Progression through the care cascade at 1 and 3 months:

- a. HIV and HCV: confirmation of diagnosis and baseline laboratory testing at 1 month (HIV: confirmatory serology, viral load and genotyping; HCV: qualitative RNA measurement and genotyping)
 - b. HCV: liver fibrosis assessment at 3 months.
 - c. HIV and HCV: initiation of treatment for HIV at 1 month and HCV at 3 months.
6. Organization of services: nursing time to inform the patient, time for results management, mode of communication used to announce results, number of tests performed per period and associated costs.

Data collection

The number of eligible patients during the study period will be determined via data from the SIURGE system. Completed triage sheets will identify the number of known patients for each virus, the number of refusals, the number of patients not approached for the study and basic patient demographics (age, zip code).

The hospital computer system (OACIS) will be used to obtain the results of screening tests (including confirmatory tests performed at the LSPQ as part of an initial screening test) for all screened patients as well as management results for patients included in the cohort of infected patients (2nd confirmatory serology, viral load and genotyping for HIV, qualitative RNA, genotyping and liver fibrosis assessment for HCV). Management and initiation of treatment will be determined in OACIS or by follow-up calls 1 and 3 months after diagnosis depending on whether the patient has decided to be followed at the CHUM or not. The time required to notify patients of results will be recorded in the research nurse's observation sheets, as will the means of communication used to reach the patient. Test costs will be extracted from the Répertoire québécois et système de mesure des procédures de biologie médicale.¹⁹

Statistical Considerations

Sample size

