The sample size was based on the threshold prevalence of newly diagnosed HIV infection that warrants the implementation of a routine HIV testing program (1/1000 according to the CDC). Assuming a prevalence of undiagnosed cases of 1/1000, a study of 4,000 subjects would yield a 95% confidence interval of 0.3/1000 to 2.7/1000. For HCV, assuming a prevalence of undiagnosed cases of 1/100, we will obtain a 95% confidence interval between 0.7 and 1.3%. In 2014-2015, 110 420 consultations took place in the CHUM emergency department.²⁰ Patients were between 18 and 74 years of age in 85% of cases,²⁰ which represented 93 857 consultations per year (7821/month). Few studies have reported missed opportunities for screening in emergency department opt-out situations. One study reported 49.9% missed opportunities due to either staff oversight or patient refusal.¹¹ In other studies, patient refusal rates were in the range of 30-35%.^{8,9} Assuming a proportion of patient refusal and staff oversight of 50%, the recruitment period should be a maximum of 2 months.

Analyses

Descriptive statistics with 95% confidence intervals will be used to calculate, separately for HIV and HCV, the prevalences of new and known cases and the proportions of "opt-out" and staff adherence to testing. The prevalences of new and known HCV cases among baby boomers will be calculated in the same way. Medians and their confidence intervals will be calculated for the time required to inform the patient of the screening and for the time required to announce the result. Program costs will be presented in absolute terms and as a cost per newly diagnosed case. Liaison with a specialized team, completion of the initial workup and initiation of treatment at one month (HIV) or three months (HCV) will also be presented as proportions with their confidence intervals.

Ethical and Regulatory Considerations

Research Ethics Board

The protocol, forms and regulatory documents will be submitted to and approved by the CHUM Research Ethics Committee and Scientific Committee.

Information and consent form

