if only people who use drugs were to be screened, this would not likely be the case for the prevalence of new cases, as the screening service for people who use drugs in Montreal is already well established. Although similar projects have been carried out in the United States, it is important not to make inferences from the epidemiological data established there. The different context of care in Quebec, including free health care and possibly easier access to screening, may have a major impact on the prevalence of new cases that we will establish. Expanded screening may not be as cost-effective in Quebec as in the United States.

In terms of limitations, it is possible that patients who come to us for reasons that do not warrant blood sampling will refuse the test more often than those who need it. The former group of patients may be healthier, so there may be a bias towards an increase in the observed prevalence. Since the same situation is likely to occur in real practice, our results will still be valid. The night-time clientele may be different from the daytime clientele. It is important that nurses on different shifts adhere to the protocol in the same way to avoid bias. Training will therefore be given to all shifts. Like all serological tests, those used have a window period and may miss acute cases, thus reducing the observed prevalence of new cases. However, the tests used are those with the shortest window period available on the market. Finally, the clientele consulting the emergency room varies greatly depending on the geographic location of a hospital. The results obtained at the CHUM may not be generalizable to other hospitals and a second multicentre project will be necessary if the initial targets are met. This second phase will better establish the prevalence of new cases and the cost-effectiveness of screening in EDs serving populations with fewer traditional risk factors for HIV or HCV than CHUM.

References

2. 90-90-90. An ambitious treatment target to help end the AIDS epidemic. (Accessed 5 septembre 2016, at http://www.unaids.org/sites/default/files/media_asset/90-90-90_en_0.pdf.)

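### The overall-prevalence formula counts every disclosed known case but drops untested patients of unknown status, so it is expected to overstate prevalence among ED patients

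*Combined protocol and SAP*

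**What the plan says.** Primary objective 2 reads "To determine the overall prevalence of HIV and HCV (new cases and known cases) among the patients visiting the CHUM emergency department". Under Outcomes, primary outcome 2 is "Overall prevalence of HCV and HIV during the study period: (positive tests + known positive cases) / (tests performed + known positive cases", and secondary outcome 1b uses the same rule for HCV in baby boomers: "Overall prevalence (positive tests + known positive cases) / (tests performed + known positive cases". With P positive tests, T tests and K known positives, both are (P + K) / (T + K).

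Known status comes from the triage questions under Materials for Nurses: "Are you infected with HIV? Are you infected with HCV". Under Screening, a patient already known to have a virus is exempt from the test for it. Under Data collection, "Completed triage sheets will identify the number of known patients for each virus, the number of refusals", along with patients not approached. Refusals are used in the staff-adherence and opt-out outcomes but not in overall prevalence.

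The Sample size section reports that in other studies "patient refusal rates were in the range of 30-35" per cent, and assumes 50% for refusal and staff oversight together. The Analyses section plans descriptive proportions with 95% intervals and no weighting for untested patients. The limitations section says that healthier patients may refuse more often, so "there may be a bias towards an increase in the observed prevalence".

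**The concern.** The two kinds of patient enter by different doors. A known case needs only to answer a question; a patient of unknown status must also accept a blood test and have it done. Refusers come from the same triaged group as the known cases, yet only the refusers leave the denominator. Known cases then carry too much weight even when refusal has nothing to do with infection. This differs from the limitation the protocol admits, which needs refusers to be healthier than testers.

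At stake is one of the two primary outcomes, and the baby-boomer overall prevalence that copies its formula. The intervals would be centred on the wrong value, and a larger sample would not help.

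Patients never approached do not cause the problem, because they drop out of the known and the tested counts alike.

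**Working it through.** **The plan's own figures.** The documents give no figure for overall prevalence. The planned intervals for undiagnosed prevalence do reproduce: 4/4,000 gives 0.29–2.67 per 1000 (Agresti-Coull; stated 0.3–2.7), and 40/4,000 gives 0.69–1.31% (Wald; stated 0.7–1.3%). They concern primary outcome 1, which is not affected.

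**Algebra.** Among patients asked at triage, let k be the known-positive share, u the undiagnosed prevalence in the rest, and t the share of the rest who are tested.

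- Target: k + (1 − k)u
- Written formula: [k + t(1 − k)u] / [k + t(1 − k)]

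With k > 0 and refusal unrelated to infection, these agree only at t = 1. More generally, the target is a weighted average of the formula's value (known plus tested patients) and the undiagnosed prevalence in the untested. The formula therefore overstates whenever the untested have an undiagnosed prevalence below the formula's own value.

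**Inputs.**

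- u = 1/1000 (HIV) and 1/100 (HCV), with 4,000 tests: Sample size section.
- Refusal 30–35%, so t = 0.70–0.65: Sample size section. The 50% figure is not used because it includes oversight.
- k is not given. For illustration it is derived from the Rational section, which estimates that "44% of Canadians infected with HCV and 21% of Quebecers infected with HIV are unaware of their status". Applying those shares (s) to this ED is an assumption. Solving u(1 − k)/[k + u(1 − k)] = s gives k = u(1 − s)/[s + u(1 − s)]:
  - HIV: 0.00079/0.21079 = 0.375%
  - HCV: 0.0056/0.4456 = 1.257%
- All known cases disclose at triage (assumption).

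**Expected counts at 35% refusal.**

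| | Asked | Known | Tested | Refused | Positive | Written formula | Target |
|---|---|---|---|---|---|---|---|
| HIV | 6,177 | 23.15 | 4,000 | 2,154 | 4 | 27.15/4,023.15 = 0.67% | 0.47% |
| HCV | 6,232 | 78.3 | 4,000 | 2,154 | 40 | 118.3/4,078.3 = 2.90% | 2.24% |

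**By refusal rate.** Coverage is of the nominal 95% Wilson interval, from 40,000 simulated studies per setting.

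| Refusal | HIV ratio to truth | HIV coverage | HCV ratio to truth | HCV coverage |
|---|---|---|---|---|
| 10% | 1.09 | 92% | 1.06 | 90% |
| 30% | 1.34 | 67% | 1.23 | 40% |
| 35% | 1.42 | 54% | 1.29 | 22% |

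**Varying the assumptions.**

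- Known share 0.1–5% at 35% refusal: ratio 1.27–1.50 (HIV) and 1.05–1.41 (HCV).
- Refusers' undiagnosed prevalence 0 to 2 times testers', at 35% refusal: ratio 1.54 down to 1.32 (HIV) and 1.53 down to 1.12 (HCV). The bias reverses above 0.67%/0.1%, about 6.7 times (HIV), or 2.90%/1%, about 2.9 times (HCV).
- 20% of known cases conceal and are counted as refusals, at 30–35% refusal: ratio 1.11–1.18 (HIV) and 1.08–1.13 (HCV). The bias cancels when the concealing share equals the refusal rate.

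The size for baby boomers cannot be computed, because no known share is given for that group.

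**The case against.** The net direction is not guaranteed. It needs known cases to disclose more completely than other patients accept testing, and the documents give no disclosure rate. With 10% refusal and 20% of known cases concealing and refusing, the written formula gives 0.91 (HIV) and 0.94 (HCV) times the truth. This stands, and is why the claim is that overstatement is expected under stated conditions.

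The size is not the protocol's either. Known prevalence is inferred from general-population shares, and the protocol itself warns that ED clientele varies by location. The coverage figures also depend on the interval, which the plan does not name: Wald intervals give about 79% to 69% for HIV and 46% to 27% for HCV. Both points stand. The figures are illustrative, and undercoverage remains with either interval.

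Nor is the replacement always better. With 20% concealment it gives 0.84 (HIV) and 0.89 (HCV) times the truth, further off than the written formula's 1.11 and 1.08 at 30% refusal. It needs a sensitivity range for that reason.

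For HCV, the triage question asks about infection while the screening test detects antibody. This affects both estimators equally and does not favour the written one.

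Finally, the study is descriptive, and a reader could roughly adjust the result if all counts were published. That lowers the severity, but the primary outcome as defined still does not estimate its objective.

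**Conclusion.** The concern holds. If known cases exist and disclose their status, and some patients who are asked go untested for reasons unrelated to infection, the written formula overstates overall prevalence. No section corrects this.

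In the illustration at 30–35% refusal, the excess is 0.16–0.20 percentage points for HIV and 0.52–0.66 for HCV. At 10% refusal it is small. The mechanism is certain; the size depends on known prevalence, disclosure and the infection rate among refusers, none of which the documents give.

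The hypotheses of 1/1000 and 1/100 and the sample-size intervals are unaffected, and no decision rule uses overall prevalence. It should be fixed because it is a primary outcome, but it does not undermine the study.

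**What to change.** For each virus, redefine primary outcome 2, and likewise secondary outcome 1b for HCV, as k + (1 − k) × u, where:

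- k = known positive / (known positive + tested + refused + asked but not tested)
- u = positive tests / tests performed in patients of unknown status

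Use a bootstrap or logit-scale delta-method 95% interval. At 35% refusal, under both assumptions below, the replacement has a mean ratio to truth of 1.00 and 95% coverage on the logit scale. The plain delta method falls to 90.5% for HIV at k = 0.05%, where the logit interval covers 96.1%.

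State both assumptions: u is the same in tested and untested patients, and known infections are disclosed at triage. Report a sensitivity table with undiagnosed prevalence in the untested at 0, 0.5, 2 and 3 times u, and with k replaced by k/(1 − c) for c = 10% and 20% concealment. In the illustration at 35% refusal, the replacement is closer to the truth than the written formula unless refusers' undiagnosed prevalence exceeds about 3.9 times (HIV) or 1.95 times (HCV) testers', or about 21% of known cases conceal and refuse (about 18% at 30% refusal). Adding 4 times u for HIV would take the table past the first of these points.

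The cost is the wording of two outcome definitions, one analysis line and a short table. Known cases per virus, refusals and patients not approached are already collected. Refusals must also be tallied per virus, and asked-but-untested patients found by linking triage sheets to OACIS. The reported overall prevalence will be lower.
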